##### 9.4.2.1 Chemical Name of E2006

- Test drug code: E2006
- Generic name: Lemborexant
- Chemical name: (1R,2S)-2-{[(2,4-dimethylpyrimidin-5-yl)oxy]methyl}-2-(3-fluorophenyl)-N-(5-fluoropyridin-2-yl)cyclopropanecarboxamide)
- Molecular formula: C22H20F2N4O2
- Molecular weight: 410.42

##### 9.4.2.2 Comparator Drug

Not applicable

##### 9.4.2.3 Labeling for Study Drug

Lemborexant will be labeled in accordance with text that is in full regulatory compliance with each participating country and is translated into the required language(s) for each of those countries.

##### 9.4.2.4 Storage Conditions

Study drug will be stored in accordance with the labeled storage conditions. Temperature monitoring is required at the storage location to ensure that the study drug is maintained within an established temperature range. The investigator or designee is responsible for ensuring that the temperature is monitored throughout the total duration of the study and that records are maintained; the temperature should be monitored continuously by using either an in-house validated data acquisition system, a mechanical recording device, such as a calibrated chart recorder, or by manual means, such that minimum and maximum thermometric values over a specific time period can be recorded and retrieved as required.

#### 9.4.3 Method of Assigning Subjects to Treatment Groups

Subjects will be assigned to treatments (or treatment sequences) based on a computer-generated randomization scheme that will be reviewed and approved by an independent statistician. The randomization scheme and identification for each subject will be included in the final clinical study report for this study.

#### **9.4.4 Selection of Doses in the Study**

The approved dose of LEM 10 mg was chosen based on the safety and efficacy studies from the clinical development program.

#### **9.4.5 Selection and Timing of Dose for Each Subject**

All randomized subjects will receive lemborexant 10 mg or placebo for 8 nights in each treatment period per the randomization scheme for OSA and COPD cohorts. The Treatment Periods will be separated by a washout interval of at least 14 days.

Subjects will receive the 1st dose of study treatment at the sleep laboratory within 5 min before the lights off and will remain overnight in the sleep laboratory. Subjects will be provided with the study medication to be administered for 6 consecutive nights at home, and will be instructed to take the medication immediately (within 5 minutes) before bedtime. After 6 consecutive nights of administering the study drug at home, subjects will return to the clinic and receive 8th dose of study drug at the sleep laboratory within 5 min before the lights off and remain overnight in the sleep laboratory.

#### **9.4.6 Blinding**

During the Randomization Phase, subjects and all personnel involved with the conduct and interpretation of the study, including investigators, site personnel, and sponsor staff will be blinded to the treatment codes. Randomization data will be kept strictly confidential, filed securely by an appropriate group with the sponsor or CRO and accessible only to authorized persons (eg, Eisai Global Safety) until the time of unblinding, per SOP.

A master list of all treatments and the subject numbers associated with them will be maintained in a sealed envelope by the clinical supply vendor, the IxRS vendor, and by the sponsor. In addition, master code breaker reports or envelopes identifying the treatment group of each subject number will be provided to the site and to the sponsor in sealed envelopes. These code breaker reports or envelopes are not to be opened unless an emergency occurs and knowledge of the subject's randomization code may affect his/her medical treatment. If possible, before breaking the blind, the investigator should consult with the sponsor to ascertain the necessity of breaking the code. The investigator is to record the date and time of opening the code breaker report or envelope and the reason for breaking the code. At the conclusion of the study, where possible, all unused drug supplies at the site, together with master code breaker reports or envelopes, are to be returned to the clinical supply vendor for final reconciliation and disposition.

#### **9.4.7 Prior and Concomitant Therapy**

Any medication (including OTC medications) or therapy administered to the subject during the study (starting at the date of informed consent or 90 days before first dose/administration of study drug, if appropriate) will be recorded on the Prior & Concomitant Medication case report form (CRF) or Non-Pharmacological Procedures CRF. The investigator will record on the AE CRF any AE for which the concomitant medication/therapy was administered.

Subjects with OSA will be required to abstain from using a CPAP device or dental appliance for at least 2 weeks before the screening PSG, and throughout the study (until after the EOS Visit).

Subjects must abstain from the use of recreational drugs throughout the study. No alcohol will be permitted in the clinic.

Prohibited medications should not be used during the study. A subject must not have used any prohibited prescription or over-the-counter medications within 1 week or 5 half-lives, whichever is longer, before Screening Visit 2. Prohibited medications include strong and moderate cytochrome P450 (CYP)3A inhibitors and strong and moderate CYP3A inducers. Prohibited medications also include any pharmacological treatment for insomnia disorder, including any medications (hypnotics or medications with known sedating effects) that are used for the purpose of inducing sleep or for treating OSA. These prohibitions apply even if the entire class to which that medication belongs is not prohibited (eg, anticonvulsants).

If a medication is not specified as prohibited but is in the same class as a medication and if the investigator is uncertain whether the medication has known sedating or alerting effects, the Medical Monitor must be consulted.

If a subject starts any prohibited medication or therapy, he/she must discontinue from the study, with the exception that certain prohibited medications may be used for a short duration (not to exceed 2 weeks) to treat an acute condition if this is agreed with the Medical Monitor. Note that strong and moderate CYP3A inhibitors and strong and moderate CYP3A inducers will not be permitted at any time for any duration during the study.

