#### 9.1.2 Randomization/Treatment Phase

In the Randomization Phase, subjects will be randomized into treatment sequence A or B (OSA Cohort), or treatment sequence C or D (COPD Cohort) consisting of 2 Treatment Periods, 8 nights duration each: lemborexant 10 mg and placebo, with the treatments periods separated by a washout interval of at least 14 days. Randomization will be stratified by age (adults  $\geq$ 45 and  $<$ 65 years, vs elderly  $\geq$ 65 to 90 years). A sufficient number of subjects will be randomized to ensure that, for each Cohort, 20 evaluable adult subjects and 10 evaluable

elderly subjects complete the study. Within each age stratum, subjects will be randomized to 1 of the 2 treatment sequences in a 1:1 ratio and enter Treatment Period 1.

Subjects will remain overnight in the sleep laboratory. Bedtime (lights off) will be at the MHB that was used at the second Screening Visit (Visit 2). Subjects will receive study drug immediately (within 5 minutes) before lights off. The PSG recording will begin at lights off and will continue for 8 hours (until lights on). The following morning, a PK blood sample will be collected and vital signs assessed, as indicated in the Schedule of Procedures/Assessments ([Table 4](#)).

Subjects will be provided with study medication to be administered for 6 consecutive nights at home, and will be instructed to take the medication immediately (within 5 minutes) before bedtime. Subjects will also be instructed on study restrictions related to prohibited medications/drugs, caffeine and alcohol, and the prohibitions regarding the use of continuous positive airway pressure (CPAP) device or dental appliance. If  $\text{SpO}_2 < 80\%$  for  $\geq 20\%$  of TST during the first night of treatment, the subject must be early terminated. Subjects may leave the clinic after the investigator determines that it is safe for them to do so. Subjects will be instructed to promptly contact study physician in case of any new complaints or exacerbation of current symptoms.

On Day 5 (with a window of  $\pm 2$  days to accommodate a weekend), the site will telephone the subject to assess AEs and record concomitant medications. If any AE is clinically significant and requires follow-up, an Unscheduled Visit should be arranged as soon as possible.

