After 6 consecutive nights of administering study drug at home, subjects will return to the clinic and receive 8th dose of study drug at the sleep laboratory within 5 min before the lights off and will remain overnight in the sleep laboratory. Subjects will undergo the same procedures as on Day 1 (including urine pregnancy test for female subjects of childbearing potential and urine drug test), in addition to which, a blood sample for pre-dose (trough) PK will be taken within 1 hour before dosing. The following morning, blood samples will be collected for PK, and exploratory biomarker assessments. Routine safety assessments will also be conducted, as indicated in the Schedule of Procedures/Assessments ([Table 4](#)). Subjects will be instructed on study restrictions related to prohibited medications/drugs, alcohol and caffeine, and the prohibitions regarding the use of CPAP device or dental appliance. Subjects may leave the clinic after the investigator determines that it is safe for them to do so.

After Treatment Period 1, there will be a washout interval of at least 14 days. After the washout interval, subjects will return to the clinic for Treatment Period 2, which will follow the same schedule and procedures as did in Treatment Period 1, including re-review of inclusion and exclusion criteria, and oxygen desaturation. However, spirometry will only be performed during the Screening Period (revised per Amendment 01).

At specified visits throughout the Prerandomization Phase and the Randomization Phase, all subjects will undergo routine safety assessments, including 12-lead ECG, physical examination, vital signs, weight, hematology, blood clinical chemistry analysis, urinalysis,

reporting of AEs, and assessment of suicidality. At each clinic visit, subjects will also undergo a urine drug screen.

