#### 9.1.2.1 Follow-Up Period

During the Follow-up Period (approximately 28 days), subjects will not receive any treatment. At the end of the Follow-up Period, subjects will return to the clinic for an EOS visit at which safety will be assessed.

If subjects discontinue prematurely, they will undergo an Early Termination (ET) Visit and will then be followed for 28 days, after which, an EOS visit should be scheduled.

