## **Inclusion and Exclusion Criteria for the OSA and COPD Cohorts**

The eligibility criteria in Study 113 are largely standard for safety studies in subjects, with particular criteria that are standard for studies of sleep agents (exclusion of significant periodic limb movement disorder or parasomnias; certain restrictions on habitual bedtime). Insomnia disorder is not specifically excluded unless subjects habitually sleep less than 5.5 hours. The screening PSG will be key for inclusion, since subjects tend to sleep less well in a sleep laboratory than at home. This is important since the AHI tends to be higher during REM sleep, which is more frequent during the second half of the night, the time when elderly poor sleepers tend to be awake.

Of note, CPAP and oral devices will be prohibited throughout the study. The study requires uncorrected values for AHI. The phenomenon of “CPAP washout” has been reported, in which, following cessation of CPAP use, AHI increases gradually over days or weeks ([Vroegop, et al., 2015](#)). Although the existence of this phenomenon is not universally accepted, there is no doubt that daytime sleepiness increases when CPAP is stopped, and those patients with OSA will accommodate to the increased levels of sleepiness, but that takes time, and the duration varies among patients. To avoid dosing with LEM (which may cause somnolence during the day in some subjects) against an unstable baseline of daytime sleepiness, Study 113 requires that CPAP not be used from 2 weeks before the screening PSG until the end of the second treatment period. This should not interfere with the medical care of OSA patients, or be a significant impediment to recruitment; many patients do not tolerate CPAP, such that non-compliance rates are high, as stated above. Further, the exclusion criterion specifies that there must not be a requirement that subjects use CPAP during the study, thereby excluding any for whom CPAP is a medical necessity. Whether subjects had been prescribed CPAP or other treatments for OSA in the past will be noted at Screening.

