15. History of drug or alcohol dependency or abuse within approximately the last 2 years
16. Use of illegal recreational drugs (includes marijuana, regardless of whether prescribed for medicinal use)
17. Currently enrolled in another clinical study or used any investigational drug or device within 28 days or 5 $\times$  the half-life, whichever is longer preceding informed consent
18. Previously participated in other clinical trial of lemborexant
19. Exposure within the last 14 days to an individual with confirmed or probable corona virus disease 2019 (COVID-19) or symptoms within the last 14 days that are on the most

recent Centers for Disease Control and Prevention (CDC) list of COVID symptoms or any other reason to consider the subject at potential risk for an acute COVID-19 infection (revised per Amendment 01)

Additional Exclusion Criteria (OSA Cohort)

20. SpO2 <80% for  $\geq 5\%$  of TST during the screening PSG
21. Use of a CPAP device or dental appliance within 2 weeks of the screening PSG, and does not agree to abstain from the use of a CPAP device or dental appliance from the Screening Visit through the last study visit
22. Current evidence of a clinically significant, active respiratory disorder other than OSA. This includes bronchiectasis, emphysema, asthma, COPD or any other pulmonary disorder identified by review of medical history, physical examination, and which in the opinion of the investigator, could compromise the subject's safety or interfere with study assessments.
23. Current evidence of other clinically significant disease (eg, psychiatric disorders, disorders of the gastrointestinal tract, liver, kidney, respiratory system, endocrine system, hematological system, neurological system, cardiovascular system, or a congenital abnormality), malignancy within the past 5 years (other than adequately treated basal cell carcinoma or in situ carcinoma of the cervix), or chronic pain that in the opinion of the investigator could affect the subject's safety or interfere with the study assessments. Subjects for whom a sedating drug would be contraindicated for safety reasons because of the subject's occupation or activities are also excluded. Subjects with insomnia disorder, who complain of difficulties with sleep onset and/or sleep maintenance, are eligible provided that they meet this criterion. Note that medications to treat insomnia are prohibited.

Additional Exclusion Criteria (COPD Cohort)

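### The protocol gives two end dates for the CPAP and dental-appliance ban; the operative one keeps OSA subjects off devices for 28 days after discharge without a stated reason

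*Protocol*

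**What the plan says.** The end of the ban is stated in several places.

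- **Section 9.4.7 and the Synopsis (Concomitant Drug/Therapy), OSA subjects:** no CPAP or dental appliance for at least two weeks before the screening PSG "and throughout the study (until after the EOS Visit".
- **Section 9.3.2, exclusions 21 (OSA) and 32 (COPD):** abstention is to run "from the Screening Visit through the last study visit".
- **Section 9.2, paragraph on eligibility for both cohorts:** it opens with "CPAP and oral devices will be prohibited throughout the study", but later states the requirement as "CPAP not be used from 2 weeks before the screening PSG until the end of the second treatment period".

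Section 9.2 also gives the reasons. One is "The study requires uncorrected values for AHI". The other is to avoid giving lemborexant while daytime sleepiness is still shifting after CPAP has been stopped.

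Section 9.1.2 has staff remind subjects at the Day 8 visit of the study restrictions "and the prohibitions regarding the use of CPAP device or dental appliance". Treatment Period 2 is to follow the same procedures.

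For a subject with SpO2 below 80% for at least 20% of TST "during the first night of treatment, the subject must be early terminated". Under Section 9.1.2.1, subjects who stop early are handled as follows: "they will undergo an Early Termination (ET) Visit and will then be followed for 28 days", ending with an EOS visit.

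**The concern.** The protocol contradicts itself on when a patient with moderate to severe OSA may go back to device treatment. The longer date is the operative one, because the Synopsis, Section 9.4.7 and exclusion 21 share it. Nothing in the documents explains why the ban should continue through a follow-up period with no study drug and no PSG.

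What is at stake is subject protection and consistent instructions, not inference. An OSA subject who would otherwise use a device stays untreated for about four more weeks. A site working from Section 9.2 and a site working from Section 9.4.7 could tell subjects different things at discharge. Subjects terminated early for desaturation are left in an unclear position, since no text expressly lifts the ban for them.

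The harm is not claimed for the COPD cohort, which requires AHI below 15 at screening.

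**Working it through.** **Inputs.** Target days from Protocol Table 4: Screening Visit 1 on Day -21 to -8; screening PSG on Day -15 to -2; first dose on Day 1; Period 2 first dose on Day 23; last dose and last PSG on Day 30; discharge on Day 31; EOS on Day 59. There is no Day 0, so Day -k to Day d is k + d - 1 days.

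**1. The protocol's own follow-up length.** 59 - 31 = 28 days, which matches the approximately 28 days in Section 9.1.2.1. Counted from the last dose and PSG, 59 - 30 = 29 days. The washout may be extended by up to 2 days, which moves later visits together and leaves the 28 days unchanged.

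**2. Do the stated purposes reach those 28 days?**

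| Purpose in Section 9.2 | Last day it applies | Reaches follow-up? |
|---|---|---|
| AHI measured without device correction | Day 30, last PSG | No |
| No dosing against unstable daytime sleepiness | Day 30, last dose | No |

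Follow-up involves no study treatment and ends in a safety visit.

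**3. Length of abstention, in-study days from Screening Visit 1.**

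- To EOS: 21 + 59 - 1 = 79, or 8 + 59 - 1 = 66.
- To Day 31: 21 + 31 - 1 = 51, or 8 + 31 - 1 = 38.
- Share falling after discharge: 28/79 = 35% to 28/66 = 42%.

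**4. Including the two-week lead-in before the screening PSG.**

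- To EOS: 14 + (15 + 59 - 1) = 87, or 14 + (2 + 59 - 1) = 74.
- To Day 31: 14 + (15 + 31 - 1) = 59, or 14 + (2 + 31 - 1) = 46.
- Share falling after discharge: 28/87 = 32% to 28/74 = 38%.

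The percentage depends on where counting starts; the 28 days do not.

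**5. Early termination after the first night of a period.** Assuming the Early Termination Visit is the next morning at target dates, the unclear interval is Day 2 to Day 2 + 28 = 30 in Period 1, or Day 24 to Day 24 + 28 = 52 in Period 2.

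**6. Adverse-event windows under SAP Section 5.6.2.** Period 1 runs from Day 1 to predose on Day 23, so 23 - 1 = 22 days. Period 2 runs from Day 23 to Day 59, so 59 - 23 = 36 days.

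The documents do not say how many OSA subjects would otherwise use a device, so no subject-day total can be given.

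**The case against.** **The conflict is one sentence.** Every operative text points to EOS, and the outlier sits in a design discussion whose own paragraph opens with the longer ban. This is largely right, and divergent site practice is a possibility rather than a demonstrated fact. But that sentence gives an explicit end date, and the reassurance that patient care will not suffer follows directly from it. Aligning only that sentence would remove the contradiction and leave the extra month unexplained.

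**A reason can be imagined.** Period 2 adverse events are counted to the final visit, so constant device status would keep follow-up uniform, and other restrictions also run for the whole study. This is the best counterargument, and the cost it names is real: Period 1 follow-up would be off device and Period 2 follow-up partly on. The documents never give this reason, however, and the two windows already differ in length (22 against 36 days).

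**Drug effect may outlast the last dose.** The protocol uses a washout of at least 14 days. Section 9.2 speaks of dosing, though, and even a 14-day allowance ends on Day 30 + 14 = 44, leaving 59 - 44 = 15 days unexplained.

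**Risk is limited.** Section 9.2 says that anyone who medically needs CPAP is excluded. Exclusion 21 contains no such wording, but exclusions 9, 12, 20 and 23, the SpO2 entry threshold of 94% and the right to withdraw do limit the risk. They do not justify the extra month.

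**The remaining limbs are softer.** That the Day 31 instruction would repeat the ban is inferred from Period 2 following Period 1 procedures, and the consent wording was not available to me. For early terminators, Section 9.5.5 already requires appropriate medical treatment, and the only stated penalty, discontinuation, has no force. That part is an ambiguity, not a bar.

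**Conclusion.** The point holds. The current protocol carries two end dates, and the one sites would apply extends device abstention 28 days past the Day 31 discharge, beyond both purposes it states. That is 35% to 42% of in-study abstention, or 32% to 38% if the two-week lead-in is counted. These figures assume Table 4 target days, and they matter only to OSA subjects who would otherwise use a device.

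There is no effect on power, the significance level, the PD Analysis Set or any PSG or oximetry endpoint, because no PSG follows Day 30. The change is worth making as an inexpensive gain in subject protection and clarity; it is not a threat to the trial's conclusions.

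**What to change.** - In the Synopsis, Section 9.4.7, exclusion 21 and the opening sentence of the Section 9.2 paragraph, end abstention at discharge after the final Period 2 PSG (Day 31) or at the Early Termination Visit, whichever comes first. State that device use may then resume. Change exclusion 32 in the same way, for consistency only.
- In Section 9.1.2, make the Period 2 discharge instruction tell subjects they may resume, instead of repeating the prohibition.
- Record resumption on the Non-Pharmacological Procedures CRF already named in Section 9.4.7, and list resumption dates beside follow-up adverse events.
- If the sponsor prefers the longer ban, it should state the reason and correct Section 9.2 to match.

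The cost is a protocol amendment, revised consent wording and one added listing. Device status will vary among OSA subjects during follow-up, which slightly complicates reading Period 2 adverse events; the listing of resumption dates addresses that.

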#### **9.4.8 Prohibitions and Restrictions During Study Period**

##### **9.4.8.1 Food and Water**

Not applicable

##### **9.4.8.2 Beverage and Other Restrictions**

Subjects must forego alcohol on day of PSG and to limit alcohol intake to no more than 2 alcohol-containing drinks per day (females) or 3 alcohol-containing drinks per day (males) on all non-PSG days for the duration of his/her participation in the study. Alcohol will not be permitted in the sleep laboratory. Caffeine will be permitted in limited quantities during the study. Subjects will be advised to limit caffeine consumption to  $\leq 4$  cups of caffeinated beverages per day, or  $\leq 400$  mg caffeine per day. They will be instructed to avoid caffeine after 13:00 on days when they are scheduled for a PSG recording and after 18:00 on all other days during the study. Subjects must forgo grapefruit juice during the duration of the study.

